#### **10.1.5 Sensitivity Analysis of Overall Survival using Imputed Death Dates**

As up to 10% of the enrolled subjects are anticipated to withdraw from the study early, a sensitivity analysis of OS will be performed where the missing death dates are imputed as the last known alive date +1 for the early withdrawn subjects. Results will be summarized with median, first, and third quartiles of Kaplan-Meier estimates with corresponding 95% CIs calculated by the Brookmeyer-Crowley method with log-log transformation. The HR and a 95% CI will be estimated using a Cox proportional hazards model, stratified by the same strata used in the analysis of ORR.

The following summary will be provided:

- Overall Survival Using Imputed Death Dates

#### **10.1.6 Subgroup Analyses of the Primary Endpoint Family**

To investigate treatment effect in subgroups, independent reviewer-assessed ORR by RECIST v1.1 and OS will be analyzed for each of the following subgroups:

- Metastasis stage (M1c and Other)
- BRAF mutation status (BRAF wild type and BRAF mutation positive)
- Duration of prior anti-PD-1 therapy ( $\geq 12$  weeks and  $< 12$  weeks)
- Region (US and non-US)

Idera Pharmaceuticals, Inc.  
 Statistical Analysis Plan  
 Protocol Number: 2125-MEL-301

- 
- Baseline ECOG (0 and  $\geq 1$ )
  - Baseline LDH (Normal:  $\leq$  ULN and Abnormal:  $>$  ULN)
  - Baseline LDH ( $\leq$  ULN, ULN to  $\leq 2x$  ULN,  $> 2x$  ULN)
  - Baseline Neutrophil/Lymphocyte Ratio ( $< 2.5$  and  $\geq 2.5$ )
  - Subjects who used CYP substrate concomitant medications and subjects who did not use CYP substrate concomitant medications

The subgroup summaries for ORR by RECIST v1.1 with 95%, two-sided CIs using the Wald's binomial method will be provided for each treatment arm within each subgroup. The subgroup summaries of OS will be summarized by treatment arm within each subgroup with median, first, and third quartiles of Kaplan-Meier estimates with corresponding 95% CIs calculated by the Brookmeyer-Crowley method with log-log transformation.

The following tables and figures will be provided for subgroup analyses:

- Subgroup Analyses of Objective Response Rate
- Subgroup Analyses of Overall Survival
- Forest Plot of Proportion Differences for Objective Response Rate by Subgroup
- Forest Plot of Hazard Ratios for Overall Survival by Subgroup

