8.2. Duration of Study

8.2.1. Treatment Duration

The Treatment Phase of the study is 10 weeks for subjects assigned to Arm A and 24 weeks for subjects assigned to Arm B.

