## 9.5 CONCOMITANT MEDICATIONS

Concomitant medications will be coded using the World Health Organization (WHO) Drug Dictionary Version B3 Sep 2020. A concomitant medication is defined as any drug or substance administered between the time of the first dose of study treatment and 30 days from the date of the last dose of study treatment, or taken to treat SAEs, irAEs, AEs of Grade 3 or above that occurred within 90 days of the last dose of study treatment, or taken to treat Grade 3 or above treatment-related AEs and SAEs that occurred during either the Active or Survival follow-up periods. This includes medications that were started prior to screening if their use continued during dosing. If the start date or end date of concomitant medication is partial, use the imputation rules defined in [Section 8.1.2](#) to impute the date and determine if the medication was concomitant.

In the summary of concomitant medications, each subject is counted once within each unique term. For example, if a subject takes Amoxicillin on two separate occasions, the subject is counted only once under the ingredient “Amoxicillin”.

The summary of concomitant medications using the Safety Set will show the number and percentage of subjects taking concomitant medications by therapeutic class and preferred term (PT). Anatomical Therapeutic Chemical (ATC) Level 4 will be used for the listing and summary.

Idera Pharmaceuticals, Inc.  
 Statistical Analysis Plan  
 Protocol Number: 2125-MEL-301

A similar summary will also be generated for concomitant medications that were used to treat immune-related adverse event as recorded on the Concomitant Medication eCRF page.

Another summary will be generated by category of concomitant immune-modulating medications that were used to treat irAEs. These medication categories include thyroid hormone replacement therapies, systemic steroids, and immune-suppressants. Thyroid hormone replacement therapies will be identified by WHO drug ATC prefix H03, systemic steroids by WHO drug ATC prefix H02, and immuno-suppressants by WHO drug ATC prefix L04. Any medications with one of these prefixes that were indicated on the Concomitant Medication eCRF page as being used to treat irAEs will be included in this summary by preferred term under the corresponding category.

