Cancer treatments including, but not limited to, radiotherapy, anticancer treatment, and surgery that occurred after the start of study treatment and were received during the study will be summarized separately. If a subject received more than one type of cancer treatment, he/she will be counted under each of them in the summary. The best overall response from these cancer treatments and procedures will be included in the summary. Biopsies and other diagnostic procedures will not be considered as cancer treatment.

IMO-2125 is a cytokine modulator that may indirectly affect cytochrome P450 (CYP) production or activity, and subsequently affect the exposure to CYP substrates. Therefore, increased AEs or decreased efficacy may occur in patients concurrently administered CYP-sensitive substrates or substrates with a narrow therapeutic range. Any concomitant medications identified as CYP-sensitive substrates or substrates with a narrow therapeutic range will be summarized and listed including any AE(s) that started during the duration of the treatment. The medications of interest are as follows:

Drug Category	Preferred Term
Sensitive CYP3A4 substrates	budesonide, buspirone, eplerenone, eletriptan, felodipine, fluticasone, lovastatin, midazolam, saquinavir, sildenafil, simvastatin, triazolam, vardenafil
CYP3A4 substrates with a narrow therapeutic range	alfentanil, astemizole(a), cisapride(a), cyclosporine, diergotamine, ergotamine, fentanyl, pimozide, quinidine, sirolimus, tacrolimus, terfenadine(a)
Sensitive CYP1A2 substrates	duloxetine, alosetron
CYP1A2 substrates with a narrow therapeutic range	theophylline, tizanidine

Idera Pharmaceuticals, Inc.  
 Statistical Analysis Plan  
 Protocol Number: 2125-MEL-301

Drug Category	Preferred Term
Sensitive CYP2C8 substrates	repaglinide
CYP2C8 substrates with a narrow therapeutic range	paclitaxel
CYP2C9 substrates with a narrow therapeutic range	warfarin, phenytoin
Sensitive CYP2C19 substrates	omeprazole
CYP2C19 substrates with a narrow therapeutic range	s-mephenytoin
Sensitive CYP2D6 substrates	desipramine
CYP2D6 substrates with a narrow therapeutic range	thioridazine

The following summaries will be provided:

- Concomitant medications
- Concomitant medications for irAEs by category (thyroid hormone replacement medications, systemic steroids, immune-suppressants)
- Cancer treatments and surgeries after the start of study treatment

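### The CYP-substrate subgroup for ORR and OS is defined by medication use after randomization, over a planned window 14 weeks longer in Arm B, so membership can depend on arm and outcome

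*SAP*

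**What the plan says.** The last entry in the subgroup list of SAP 10.1.6 reads "Subjects who used CYP substrate concomitant medications and subjects who did not use CYP substrate concomitant medications". It has no time anchor. ECOG, LDH and neutrophil/lymphocyte ratio in the same list are labelled as baseline values. Stage, BRAF status, prior anti-PD-1 duration and region are fixed at entry. Results go into Tables 14.2.1.4.8 (ORR) and 14.2.3.4.8 (OS), both on the ITT set, and the section also plans subgroup forest plots of ORR differences and hazard ratios.

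The medication definition is in SAP 9.5:

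- The core window is "any drug or substance administered between the time of the first dose of study treatment and 30 days from the date of the last dose".
- It is extended by drugs "or taken to treat SAEs, irAEs, AEs of Grade 3 or above that occurred within 90 days of the last dose of study treatment", and further for drugs treating later treatment-related Grade 3 or above events and SAEs.
- On earlier use: "This includes medications that were started prior to screening if their use continued during dosing". Nothing limits the subgroup to such use.
- CYP substrates are picked from this pool: "Any concomitant medications identified as CYP-sensitive substrates or substrates with a narrow therapeutic range will be summarized". The matching listing in SAP 16.2 refers to use during the study.

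Protocol 8.2.1 states: "The Treatment Phase of the study is 10 weeks for subjects assigned to Arm A and 24 weeks for subjects assigned to Arm B". Protocol 8.3.1 names progression, death and intolerable AE among the reasons for stopping early.

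**The concern.** A subject has to stay on treatment, and alive, to have time to be recorded as a user. That time is longer by design in Arm B. The first scan is at Week 12, after Arm A's last planned dose but before three of Arm B's doses, so tumour response can lengthen the window in Arm B and can hardly do so in Arm A. A randomized subject who is never dosed has no first dose and can only be a non-user.

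The substrate list adds other possible links. Budesonide, cyclosporine and tacrolimus could be given for immune-related events, and midazolam or fentanyl around a deep injection. These uses are inferences from the drug names; the SAP does not state them.

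What is at stake is how two subgroup tables and two forest plots are read. An estimate within a group formed after randomization would sit beside valid baseline subgroups, with nothing to warn the reader.

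**Working it through.** **1. Planned window.** The dosing weeks are in Protocol 9.3.3; count days from the Week 1 dose.

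- Arm A: last dose Week 10, (10 − 1) × 7 = 63 days; 63 + 30 = 93.
- Arm B: last dose Week 24, (24 − 1) × 7 = 161 days; 161 + 30 = 191.
- Difference: 191 − 93 = 98 days = 14 weeks, matching the 10 versus 24 weeks of Protocol 8.2.1.

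This is the difference for subjects who complete dosing.

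**2. ORR, closed form.** The documents give no CYP use rates. Assume 20% use at baseline, new starts at h = 5% or 10% per month, and a true ORR of 18% in both arms. For a window of d days:

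P(user) = 1 − 0.8 × exp(−h × d / 30.4375)

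First suppose every Arm B non-responder stops after the Week 11 dose, so d = 70 + 30 = 100, while responders have d = 191. At h = 5%:

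- Responders: P(user) = 0.415. Non-responders: 0.321.
- ORR in users = 0.18 × 0.415 / (0.18 × 0.415 + 0.82 × 0.321) = 22.1%.
- ORR in non-users = 0.18 × 0.585 / (0.18 × 0.585 + 0.82 × 0.679) = 15.9%.
- Gap: 6.2 points. At h = 10%: 22.9% versus 14.0%, gap 8.9.

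The gap depends strongly on how long non-responders are dosed. For those stopping after Week 16, d = 105 + 30 = 135.

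| Arm B non-responders | Gap at h = 5% | Gap at h = 10% |
|---|---|---|
| All stop after Week 11 | 6.2 | 8.9 |
| Half to Week 24, rest stop after Week 11 | 3.0 | 4.4 |
| One-third to Week 24, rest stop after Week 16 | 2.3 | 3.4 |
| Half to Week 24, rest stop after Week 16 | 1.7 | 2.6 |
| Three-quarters to Week 24, rest stop after Week 11 | 1.5 | 2.2 |

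**3. Simulation with no treatment effect.** This used 400,000 subjects per arm, the same outcome law in both arms, 0-30% baseline users, 2-15% new users per 4 weeks, and a Cox hazard ratio (B versus A) within each subgroup. Use was unrelated to toxicity or procedures.

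| | Window cut by death only | Dosing also stops at progression |
|---|---|---|
| Median OS | 11.4 months | about 13.7 months |
| Mean window, A vs B | 85 vs 159 days | 77 vs 121 days |
| HR, users | 0.91-0.97 | 0.88-0.98 |
| HR, non-users | 1.01-1.19 | 1.01-1.11 |

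The hazard ratio in all subjects was 0.996-1.004 throughout. In the second setting, with true ORR 12% in both arms, the B minus A difference was +0.8 to +4.2 points in users and −0.2 to −3.3 points in non-users. The realized window difference was 74 days (10.6 weeks) and 44 days (6.3 weeks), less than the planned 14 weeks.

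**4. OS against sampling noise.** Assume 150 of the 392 deaths are in users, leaving 242 in non-users. SE(log HR) in users ≈ 2/√150 = 0.163, so a 95% interval around 1.0 is about 0.73-1.38. The SE of the user versus non-user contrast is √(4/150 + 4/242) = 0.21. The largest simulated contrast, log(1.183/0.935) = 0.235, is about 1.1 of those SEs.

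**The case against.** **The larger ORR gaps need a stopping rule the plan does not have.** The 6-9 point figure requires every Arm B non-responder, including those with stable disease, to stop after Week 11. Stable disease is not a listed reason for stopping (Protocol 8.3.1). Treatment may run until confirmed progression (11.1) and, at the investigator's discretion, beyond progression (9.3.3.2). This stands: 6-9 points is near a worst case, and smaller gaps are just as compatible with the text.

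**Arm A is not immune.** Early clinical progression, death or toxicity also shortens its window, and the adverse-event extension applies to both arms. This stands too.

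**Direction is open.** Drugs given for toxicity or around procedures could tie use to worse outcomes in either arm. A reader might infer that the rule always flatters Arm B users; the documents do not support that.

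**The rule need not hide an effect the SAP is seeking.** SAP 9.5 warns that "increased AEs or decreased efficacy may occur in patients concurrently administered CYP-sensitive substrates". A reader might take this as a suspected loss of ORR or OS benefit. But the sentence follows from a statement that IMO-2125 may alter exposure to the substrate drugs, so the efficacy meant may be theirs.

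**Little formal weight.** The subgroup carries no alpha, no interaction test is planned, and the OS distortion is modest against noise. Derivation details sit in dataset specifications outside these documents. All true, but neither the protocol nor the SAP contains a baseline restriction, a common window, a landmark or a time-varying rule.

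**Conclusion.** The definitional flaw holds. As written, membership is settled after randomization, over a planned window of 93 days in Arm A and 191 in Arm B that progression, death or toxicity can cut short, with never-dosed subjects placed among non-users. Randomization does not protect the ORR and OS comparisons within these groups.

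Size and direction are not established, because no use rates are given. Under the assumptions above, with no true effect, the window alone tends to favour Arm B among users: an Arm B user versus non-user ORR gap of roughly 2 to 9 points, depending on how many non-responders continue dosing, and hazard ratios of about 0.88-0.98 in users and 1.01-1.19 in non-users. Use driven by adverse events or procedures could offset or reverse that. The window bias disappears if no substrate is started or stopped after baseline.

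A reader might infer that the plan will produce a false OS interaction or that the main result is compromised. Neither follows. The primary ORR and OS tests, 454 subjects, 392 deaths and the 0.02/0.005 alpha split are untouched.

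**What to change.** In SAP 10.1.6 and Tables 14.2.1.4.8 and 14.2.3.4.8, define the subgroup as a CYP substrate from the SAP 9.5 list ongoing at first dose (at the randomization date if untreated), yes or no. State that the drug must have started before that date. Also state how start dates that SAP 8.1.2 imputes to the first dose date are classified, since these would otherwise be ambiguous. Keep on-treatment CYP use in the descriptive medication and AE outputs of SAP 9.5.

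With membership fixed this way, the expected result under no effect is a hazard ratio of 1.00 and an ORR difference of 0 in both subgroups.

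The cost is a change of SAP wording and one derivation from medication dates already collected. The downside is real: subjects who start a substrate later count as non-users, so the user group is smaller and the subgroup no longer addresses concurrent use. If on-treatment use is of interest, add an exploratory landmark analysis with the same window in both arms, or a time-varying analysis, and keep it off the baseline-subgroup forest plots.

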#### **4.5 DETERMINATION OF THE SAMPLE SIZE**

In this study, ORR and OS comprise a primary endpoint family; both have a priori hypotheses and will be tested for statistical significance. ORR will be tested first followed by OS. The fallback method for the primary endpoint family will be applied to control the study-wise Type I error rate. Under the fallback method,  $\alpha_1 = 0.02$  is assigned to the one-sided ORR test and an alpha of 0.005 is saved for the one-sided OS test. If the ORR test is significant at  $\alpha_1 = 0.02$ , this alpha is unused and will be passed to the OS test as an additional alpha of 0.02, giving a total alpha for the OS test of 0.025.

With 454 subjects planned with a 1:1 randomization ratio, this test will have 90% statistical power (calculated based on chi-square test) to demonstrate an increase in the ORR from the expected response of 12% for ipilimumab alone to 24% for the IMO-2125 + ipilimumab combination, at a 0.02 one-sided level of significance.

A sample size of 454 subjects also provides 90% power to test the alternative hypothesis of  $HR \leq 0.677$  at an  $\alpha$  of 0.005 (one-sided). The HR of 0.677 corresponds to an improvement in the median survival from 11.4 months (the historical control for ipilimumab alone) to 16.85 months with the IMO-2125 + ipilimumab combination. The number of required deaths to reach the 90% power is 392.

The OS power calculations are based on log-rank test and assume that the trial will have ~20 months of uniform accrual, an overall study duration up to 56 months, and a 10% drop-out rate. If a total alpha of 0.025 is available for the OS significance test under the fallback

Idera Pharmaceuticals, Inc.  
Statistical Analysis Plan  
Protocol Number: 2125-MEL-301

---

method, then this test will have 90% power to test the alternative hypothesis of  $HR \leq 0.72$  at an  $\alpha$  of 0.025 (one-sided). This corresponds to an improvement in the median survival from 11.4 months (the historical control for ipilimumab alone) to 15.8 months with the IMO-2125 + ipilimumab combination.

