## **10.1 ANALYSIS OF THE PRIMARY ENDPOINT FAMILY**

### **10.1.1 Independent Reviewer-Assessed ORR by RECIST v1.1**

The final and sole analysis of ORR assessed by blinded independent review using RECIST v1.1 will test the response proportions of the two treatment arms using a stratified Cochran-Mantel-Haenszel (CMH) test for two proportions by the randomized strata as defined in [Section 9.4](#). To allow for adequate time for response and confirmation, the analysis of ORR will take place no sooner than when all randomized subjects completed scheduled study treatment and completed at least 28 weeks on the study; prematurely discontinued study treatment and completed at least 28 weeks on the study; or withdrew, were lost to follow-up, or died before completing at least 28 weeks on the study.

The generic SAS procedure call is:

```
proc freq data=<dataset name>;
  tables strata*response*treatment / cmh ;
run;
```

ORR is defined as the percentage of subjects achieving a CR or PR out of the total number of subjects included in the analysis population. The CR or PR must occur prior to PD and the start of any subsequent anticancer therapy. Subjects with not evaluable, unknown, or missing best response will be handled as non-responders; i.e., they will be included in the denominator when calculating the ORR. The independent reviewer-assessed best overall response and ORR by RECIST v1.1 with 95%, two-sided, confidence intervals (CIs) using the Wald's binomial method will be provided for each treatment arm. The percentage difference of ORR between the two treatment arms with a 95%, two-sided CI, and the p-value from the stratified CMH test will be provided. In support of ORR analysis, the

Idera Pharmaceuticals, Inc.  
Statistical Analysis Plan  
Protocol Number: 2125-MEL-301

---

summary statistics for duration of active follow-up times for all subjects will be provided (see the summary under subject disposition).

The following summary and figures will be provided:

- Independent Reviewer-Assessed Response by RECIST v1.1
- Swimmer's Plot of Independent Reviewer-Assessed Response by RECIST v1.1 for ORR Responders
- Waterfall Plot of Maximum Percent Reduction from Baseline in Individual Sum of the Longest Diameters of Target Lesions, Assessed by Independent Reviewer
- Spider Plot of Individual Percent Change from Baseline in Sum of the Longest Diameters of Target Lesions Over Time, Assessed by Independent Reviewer

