#### **10.2.4 Durable Response Rate**

The durable response rate will be derived separately for the assessments by blinded independent reviewer and the investigator. DRR will be derived using RECIST v1.1, defined as the rate of CR or PR lasting  $\geq 6$  months from the date of first instance of confirmed CR or PR response which begin during the first 12 months of treatment. The denominator will be the number of subjects included in the corresponding analysis set (e.g., ITT). The calculation for the number of days in 6 months is  $6 \times (365.25/12)$ ; the cutoff date for 6 months is therefore (scan date + 182.625).

Summaries will include DRR by RECIST v1.1 with corresponding 95%, two-sided CIs using the Wald's binomial method for each treatment arm.

Summaries of DRR are included within the following summary outputs:

- DRR based on Independent Reviewer-Assessed ORR by RECIST v1.1
- DRR based on Investigator-Assessed ORR by RECIST v1.1

Note: DRR analyses are included in the Independent Reviewer-Assessed Response and Investigator-Assessed Response by RECIST v1.1 tables.

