#### **10.2.5 Disease Control Rate**

The disease control rate (DCR) is defined as the percentage of subjects achieving a confirmed CR, PR, or SD out of the total number of subjects included in the analysis population. The CR, PR, or SD must occur prior to PD and the start of any subsequent anticancer therapy. Subjects with not evaluable, unknown, or missing best response will be handled as non-responders; i.e., they will be included in the denominator when calculating the DCR. The independent reviewer-assessed DCR by RECIST v1.1 with 95%, two-sided CIs using the

Idera Pharmaceuticals, Inc.  
Statistical Analysis Plan  
Protocol Number: 2125-MEL-301

---

Wald's binomial method will be provided for each treatment arm. A similar summary will be provided using the investigator-assessed DCR by RECIST v1.1.

The following summaries will be for DCR:

- Independent Reviewer-Assessed DCR by RECIST v1.1
- Investigator-Assessed DCR by RECIST v1.1

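### Wald intervals for response proportions cover poorly in small ORR subgroup arms near the 12% control rate and collapse to [0, 0] when nobody responds; full-arm intervals are little affected

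*SAP*

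**What the plan says.** The SAP names the Wald binomial interval in four places.

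- Independent-review ORR by arm (10.1.1): "two-sided, confidence intervals (CIs) using the Wald's binomial method will be provided for each treatment arm".
- ORR by arm within each subgroup (10.1.6): "The subgroup summaries for ORR by RECIST v1.1 with 95%, two-sided CIs using the Wald's binomial method". Nine subgroup definitions are listed.
- DRR (10.2.4): "Summaries will include DRR by RECIST v1.1 with corresponding 95%, two-sided CIs using the Wald's binomial method for each treatment arm".
- DCR (10.2.5): "Wald's binomial method will be provided for each treatment arm. A similar summary will be provided using the investigator-assessed DCR by RECIST v1.1".

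The SAP gives no alternative interval, no rule for zero responders and no truncation rule. It asks for 95% intervals but names no method for the ORR difference (10.1.1) or for investigator-assessed ORR and its difference (10.2.1). Nor does it name one for the forest plot of ORR differences by subgroup (10.1.6).

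The planning rates are in SAP 4.5: "expected response of 12% for ipilimumab alone to 24% for the IMO-2125 + ipilimumab" combination. The size is there too: "With 454 subjects planned with a 1:1 randomization ratio, this test will have 90% statistical power (calculated based on chi-square test"), with the test run for the "combination, at a 0.02 one-sided level of significance". The decision on ORR rests on the stratified CMH test, not on any of these intervals.

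**The concern.** The Wald interval takes its standard error from the observed proportion. When few subjects respond, that standard error is too small and the interval is too short. With no responders it is zero and the interval has no width. With one or two responders in a small cell the lower limit falls below zero.

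The control arm is planned at 12%, and ORR is to be shown by arm within nine subgroup definitions, so some cells could hold only a handful of responders. At stake are the per-arm error bars for a primary endpoint by subgroup. They would overstate what a small subgroup shows, and a printed [0, 0] carries no usable information about the response rate there.

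**Working it through.** **Inputs.** 227 per arm (454 randomized 1:1), ORR 12% and 24%, and the interval method, all from the SAP sections above. The documents give neither subgroup sizes nor expected DRR and DCR, so those values are assumptions.

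**1. The plan's own figure.** Power of the two-proportion test, with pooled rate 0.18:

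Φ{[(0.24 − 0.12)√227 − z₀.₉₈ √(2 × 0.18 × 0.82)] / √(0.12 × 0.88 + 0.24 × 0.76)}
= Φ{(1.808 − 2.054 × 0.543) / 0.537} = Φ(1.29) = 90.1%.

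The stated 90% is reproduced. The documents give no coverage figure to reproduce.

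**2. Definition of coverage.** For n subjects and true rate p, exact coverage is the sum of the binomial probabilities of every count x whose interval contains p. With p̂ = x/n and z = 1.96:

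- Wald: p̂ ± z√(p̂(1 − p̂)/n).
- Wilson: [p̂ + z²/2n ± z√(p̂(1 − p̂)/n + z²/4n²)] / (1 + z²/n).

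**3. One cell by hand: n = 11, p = 12%.**

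| x | Wald interval | contains 12%? |
|---|---|---|
| 0 | 0 to 0 | no |
| 1 | −7.9% to 26.1% | yes |
| 2 | −4.6% to 41.0% | yes |
| 3 | 1.0% to 53.6% | yes |
| 4 | 7.9% to 64.8% | yes |
| 5 | 16.0% to 74.9% | no (nor do higher counts) |

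P(x = 0) = 0.88¹¹ = 24.5% and P(x ≥ 5) = 0.6%, so coverage is 100 − 24.5 − 0.6 = 74.9%. Nearly all of the loss comes from the zero-responder case.

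**4. Full arms, n = 227.**

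- ORR: Wald covers 93.5% at 12% and 95.5% at 24%; Wilson covers 94.8% and 95.7%. With 27 responders of 227, Wald gives 7.7 to 16.1% and Wilson 8.3 to 16.8%.
- DRR, assumed rates: 90.2% at 3%, 92.1% at 6%, 94.0% at 8%, 93.9% at 10%.
- DCR, assumed rates: 94.8% at 30%, 93.9% at 35%, 95.1% at 40%, 95.4% at 50%.

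**5. Subgroup arms.** Coverage at a single p moves in a sawtooth: at exactly 12%, Wald covers 94.3% at n = 23 and 81.3% at n = 25. Averaging over a band of true rates removes this effect. Sizes are illustrative.

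| n per arm | Wald, p 10–14% | Wilson, p 10–14% | Wald, p 22–26% | P(no responders) at 12% = 0.88ⁿ |
|---|---|---|---|---|
| 11 | 75% | 96% | 93% | 25% |
| 25 | 88% | 96% | 92% | 4% |
| 30 | 88% | 95% | 93% | 2% |
| 50 | 91% | 95% | 94% | 0.2% |
| 100 | 93% | 95% | 94% | below 0.1% |

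At n = 20 the chance of no responders is 0.88²⁰ = 8%. The shortfall is therefore concentrated in small cells near the control rate.

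**6. What replaces [0, 0].** With 0 of 11, Wilson gives 0 to 25.9% and Clopper-Pearson 0 to 28.5%. With 1 of 11, Wald starts at −7.9% and Wilson at 1.6%.

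**The case against.** The case for leaving the plan alone has real weight. No decision uses these intervals: ORR is tested by stratified CMH and secondary endpoints are descriptive (SAP 7.2). The subgroups in 10.1.6 are mostly two-way splits of 454 subjects, and at about 100 per arm Wald averages 93 to 94%. No document says that a cell will hold 10 or 15 subjects. The 5% threshold in SAP 8.2.10 (about 11 per arm, as 5% of 227) concerns randomization strata, so n = 11 is only an illustration here. The forest plot of differences also shows subgroup uncertainty, and even a simple Wald interval for 24% against 12% covers 94.7% at 30 per arm. All of this stands.

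A reader might infer that every Wald interval in the SAP falls well short of 95%. The documents do not support that. Full-arm ORR loses at most about 2 points over true rates of 10 to 26%. DCR counts stable disease as well, so it is at least as high as ORR and no low rate is planned for it. DRR is planned by arm, not by subgroup, so very poor small-sample DRR coverage matches no planned analysis. Nor is Wald prescribed for the ORR difference or for investigator-assessed ORR, where the method is simply unnamed.

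The objection does not remove the small cell. Baseline LDH is also cut three ways. The table list in SAP 16.2 has an ORR table by country where 10.1.6 has only US and non-US; if that table is produced, some cells could be small. The stated rule then gives a wrong or empty interval, and the SAP has no fallback.

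**Conclusion.** The point holds for small ORR subgroup arms near the 12% control rate and for any cell without responders. In illustrative cells of 11 to 50 subjects, average Wald coverage is about 75 to 91%, where Wilson keeps 95 to 96%. The [0, 0] result at zero responders follows from the formula and needs no assumption; how often it occurs depends on subgroup sizes that are not stated. At full-arm size the effect is minor for ORR and DRR and immaterial for DCR.

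The DRR and DCR figures rest on assumed rates. They also use the SAP's analysis-set denominator; protocol 15.4.2 can be read as restricting DRR to responders, and the two texts should be reconciled. This is an inexpensive improvement to reporting. It does not touch the stratified CMH test, type I error or the 90% ORR power.

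**What to change.** - In SAP 10.1.6 and 10.2.4, and for consistency in 10.1.1 and 10.2.5, replace the Wald interval with Wilson. Clopper-Pearson is acceptable if an interval that is never short is preferred; it is wider.
- In SAP 10.2.1, name the same single-proportion method for investigator-assessed ORR.
- For the ORR differences in 10.1.1 and 10.2.1 and the subgroup forest plot in 10.1.6, name a Newcombe or Miettinen-Nurminen interval.

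The cost is SAP wording and an option in the SAS procedure call. Limits move slightly (for 27 of 227, from 7.7–16.1% to 8.3–16.8%) and some intervals become a little wider. Sample size, data collection, alpha and the primary test stay as they are.
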